^d The Day 1 Visit should be on the same day as the last scheduled visit of the parent study (Section 9.1.1). Subjects whose Day 1 Visit is NOT within 1 day of the last scheduled visit of the parent study will repeat all Day 1 assessments. Subjects whose Day 1 Visit is within 1 day of the last scheduled visit of the parent study will NOT have to repeat any Day 1 assessments that were specified to be performed at the last scheduled visit in the parent study.

Table 3-1 Study VX20-445-119: Treatment Period and Safety Follow-up Visit									
Event/ Assessment ^a	Treatment Period					ETT Visit ^b	Safety Follow-up Visit (28 ± 7 Days After Last Dose of Study Drug ^c)	Comments	
	Day 1 ^d	Weeks 4, 8, 16, 24 (± 5 Days)	Weeks 12, 20, 28, 32, 40, 44, 52, 56, 64, 68, 76, 80, 88, 92 (± 5 Days)	Weeks 36, 48, 60, 72, 84 (± 5 Days)	Week 96 (± 10 Days)				
Standard 12-lead ECG	X	Weeks 8, 16, 24		Weeks 48, 72	X	X	X	Performed prior to any procedure that may affect heart rate (e.g., blood draws) and after subject has been at rest for at least 5 minutes (Section 11.4.5).	
Sweat chloride	X	X		Weeks 48, 72	X	X		Section 11.2.1	
Multiple-breath washout	X	X		Weeks 48, 72	X	X		Performed in multiple replicates, pre-bronchodilator, before the AM dose, and before spirometry assessment (Section 11.2.1).	
Spirometry	X	X		X	X	X	X	Performed pre-bronchodilator, before the AM dose, and at approximately the same time at each visit (Section 11.2.3).	
Pregnancy test	Urine	Serum	Urine	Serum	Serum	Serum	Serum	For all female subjects at telephone contacts, a urine pregnancy test will be performed with a home kit provided by the study site. Results of the home pregnancy test will be reported to the site by telephone (Section 11.4.2).	
Serum chemistry	X	X		X	X	X	X	Section 11.4.2	
Hematology	X	X		X	X	X	X		
Coagulation	X	Week 24		Weeks 48, 72	X	X			
Urinalysis	X			Week 48	X	X			
AEs and SAEs	Continuous from signing of the ICF through completion of study participation								Section 13.1; Completion of study participation is defined in Section 9.1.5.

Table 3-1 Study VX20-445-119: Treatment Period and Safety Follow-up Visit								
Event/ Assessment ^a	Treatment Period					ETT Visit ^b	Safety Follow-up Visit (28 ± 7 Days After Last Dose of Study Drug ^c)	Comments
	Day 1 ^d	Weeks 4, 8, 16, 24 (± 5 Days)	Weeks 12, 20, 28, 32, 40, 44, 52, 56, 64, 68, 76, 80, 88, 92 (± 5 Days)	Weeks 36, 48, 60, 72, 84 (± 5 Days)	Week 96 (± 10 Days)			

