12.3.1 General Considerations

Continuous variables will be summarized using the following descriptive summary statistics: the number of subjects (n), mean, SD, median, minimum value (min), and maximum value (max).

Categorical variables will be summarized using counts and percentages.

The **baseline value**, unless otherwise specified, for the long-term safety analysis will be the most recent non-missing measurement (scheduled or unscheduled) collected before the first dose of ELX/TEZ/IVA either in the parent study or the open label study, as applicable. The baseline value for the long-term efficacy analysis will be defined as the most recent non-missing measurement (scheduled or unscheduled) collected before the first dose of study drug in the parent study. For assessments collected in duplicate or triplicate, the baseline will be defined as the average of non-missing values.

Change (absolute change) from baseline will be calculated as Post-baseline value – Baseline value.

The **Efficacy Analysis Period** in the open-label study will include the time from the first dose of study drug in the open-label study to the last scheduled efficacy visit in the open-label study, unless otherwise specified.

The **Treatment-emergent (TE) Period** in the open-label study will include the time from the first dose of study drug in the open-label study to 28 days after the last dose of the study drug in the open-label study or to the completion date of study participation (as defined in Section 9.1.5), whichever occurs first.

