8 STATISTICAL ANALYSIS

8.1 General Considerations

The precision standards for reporting safety variables are provided in an internal Biometrics document that specifies the programming rules including the precision for derived variables.

The Schedule of Assessments is provided in Section 3 of CSP.

Continuous variables will be summarized using the following descriptive summary statistics: the number of subjects (n), mean, standard deviation (SD), median, minimum value (min), and maximum value (max).

Categorical variables will be summarized using counts and percentages. Percentages will be presented to 1 decimal place.

The **baseline value**, unless otherwise specified, for the long-term safety analysis will be the **TC safety baseline**, defined as the most recent non-missing measurement (scheduled or unscheduled) collected before the first dose of ELX/TEZ/IVA either in the parent study or the open label study, as applicable. The baseline value for the long-term efficacy analysis, unless otherwise specified, will be the **parent study baseline**, defined as the most recent non-missing measurement (scheduled or unscheduled) collected before the first dose of study drug in the parent study. For assessments collected in duplicate or triplicate, the baseline will be defined as the average of non-missing values.

Absolute change from baseline will be calculated as post-baseline value - baseline value.

Relative change from baseline will be calculated and expressed in percentage as $100\% \times (\text{Post-baseline value} - \text{Baseline value}) / \text{Baseline value}$.

Treatment-emergent (TE) Period will include the time from the first dose date of study drug in the OLE to 28 days after the last dose of the study drug in the OLE or to the date of completion of study participation (as defined in CSP Section 9.1.5), whichever occurs first.

Unscheduled visits: Unscheduled visit measurements will be included in analysis as follows:

- 1) In scheduled visit windows per specified visit windowing rules
- 2) In the derivation of baseline and last on-treatment measurements
- 3) In the derivation of maximum and minimum values during TE period, and maximum and minimum change from baseline values during TE period for safety analyses
- 4) In individual subject data listings as appropriate

Visit windowing rules: The analysis visit windows for protocol-defined visits are provided in [Appendix A](#).

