8.4.3 Electrocardiogram

For the following ECG measurements during the TE Period of OL-SS, a summary of observed values and change from baseline values will be provided at each visit (in msec): RR interval, PR interval, QT interval, and QTcF interval, QRS duration, and Heart Rate (beats per minute).

The number and percentage of subjects meeting at least 1 threshold analysis criterion during the TE Period of OL-SS will be summarized overall. The threshold analysis criteria are provided in [Appendix E](#).

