11 LIST OF APPENDICES

Appendix A: Analysis Visit Windows for Safety and Efficacy Assessment

Table 11-1 Analysis Visit Windows for Safety and Efficacy Assessments

Assessment	Visit ¹	Target Study Day	Analysis Visit Window ^{2,3,4} (in study days)
Spirometry Weight, Height and BMI as well as the corresponding z-score	Parent Study Baseline	--	≤1 corresponding to the first dose date of parent study
	OL Week 4	29	(1, 43]
	OL Week 8	57	(43, 85]
	OL Week 16	113	(85, 141]
	OL Week 24	169	(141, 211]
	OL Week 36	253	(211, 295]
	OL Week 48	337	(295, 379]
	OL Week 60	421	(379, 463]
	OL Week 72	505	(463, 547]
	OL Week 84	589	(547, 631]
	OL Week 96	673	(631, 729]
	OL Safety Follow-up	Not applicable	Use nominal visit
Sweat Chloride, LCI _{2.5} , CFQ-R	Parent Study Baseline	--	≤1 corresponding to the first dose date of parent study
	OL Week 4	29	(1, 43]
	OL Week 8	57	(43, 85]
	OL Week 16	113	(85, 141]
	OL Week 24	169	(141, 253]
	OL Week 48	337	(253, 421]
	OL Week 72	505	(421, 589]
	OL Week 96	673	(589, 729]
Hematology Serum Chemistry Pulse Oximetry Vital Signs (excluding Weight, Height and BMI as well as the corresponding z-score)	TC Safety Baseline	1	Defined in Section 8.1
	OL Week 4	29	[1, 43] where day 1 is post-dose measurement
	OL Week 8	57	(43, 85]
	OL Week 16	113	(85, 141]
	OL Week 24	169	(141, 211]
	OL Week 36	253	(211, 295]
	OL Week 48	337	(295, 379]
	OL Week 60	421	(379, 463]
	OL Week 72	505	(463, 547]
	OL Week 84	589	(547, 631]
	OL Week 96	673	(631, 687]
	OL Safety Follow-up ⁴	Not applicable	Use nominal visit
Standard 12-lead ECG	TC Safety Baseline	1	Defined in Section 8.1
	OL Week 8	57	[1, 85] where day 1 is post-dose measurement
	OL Week 16	113	(85, 141]
	OL Week 24	169	(141, 253]
	OL Week 48	337	(253, 421]
	OL Week 72	505	(421, 589]
	OL Week 96	673	(589, 687]
		OL Safety Follow-up ⁴	Not applicable

Table 11-1 Analysis Visit Windows for Safety and Efficacy Assessments

Assessment	Visit ¹	Target Study Day	Analysis Visit Window ^{2,3,4} (in study days)
Coagulation	TC Safety Baseline	1	Defined in Section 8.1
	OL Week 24	169	[1, 253] where day 1 is post-dose measurement
	OL Week 48	337	(253, 421]
	OL Week 72	505	(421, 589]
	OL Week 96	673	(589, 687]

Notes:

¹Visit name for analysis purpose is used to report data in tables and figures.

²The analysis visit windows will be applied using the following rules for both scheduled and unscheduled visits:

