Assessment	Visit ¹	Target Study Day	Analysis Visit Window ^{2,3,4} (in study days)

If the last dose date is missing or partial date is reported, the last dose date will be imputed based on, in descending order priority, the Early Treatment Termination (ETT) visit date, last visit date before the Safety Follow-up, or the last study drug administration date from EX SDTM domain, as appropriate. The imputation algorithm will ensure the imputed last dose date does not exceed the study participation end date.
 
4. Sweat Chloride: Non-missing sweat chloride concentrations from the left arm and right arm with assessment end date/time for a given arm up to 30 minutes after first dose time in treatment period will be considered for baseline.
 
5. Electrocardiogram: Baseline is defined as the most recent pretreatment measurement before the first dose of study drug in the Treatment Period. If multiple ECG measurements are obtained on the same calendar day during the TE Period,
 
 ○ For summary purpose, the calculated average ECG will be used as the ECG value on that day; ○ For threshold analysis purpose, all reported ECG values will be used. 			

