Appendix D: Imputation Rules for Missing AE dates

Imputation rules for missing or partial AE start date are defined below. If the imputed AE start date is before the study informed consent/assent date, the AE start date will be imputed using the study informed consent/assent date.

- **If only Day of AE start date is missing:**

- If the full (or partial) AE end date is NOT before the first dose date of the Treatment Period or AE end date is missing, then
 - if AE start year and month are equal to the month and year of first dose date of the Treatment Period, then impute the AE start day as the day of first dose date of the Treatment Period;
 - else impute the AE start day as 1.
- else impute the AE start day as 1.

Compare the imputed AE start date with TE period to determine whether the AE is pretreatment AE, TEAE or post-treatment AE.

- **If Day and Month of AE start date are missing:**

- If the full (or partial) AE end date is NOT before the first dose date of the Treatment Period or AE end date is missing, then
 - if AE start year is equal to the year of first dose date of the Treatment Period, then impute the AE start month and day as the month and day of first dose date of the Treatment Period;
 - else impute the AE start month as January and day as 1.
- else impute the AE start month as January and day as 1.

Compare the imputed AE start date with TE period to determine whether the AE is pretreatment AE, TEAE or post-treatment AE.

- **If Year of AE start date is missing:**

If the year of AE start is missing or AE start date is completely missing then query site and

- If the full (or partial) AE end date is NOT before the first dose date of the Treatment Period or AE end date is missing, then impute the AE start date as the first dose date of the Treatment Period;
- else impute the AE start date as the informed consent/assent date.

Imputation rules for partial AE end date are defined below:

- Impute the AE end date as min (the last day of the month, end of study participation) if day is missing, or min (Dec, end of study participation) if month is missing.

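### SAP Appendix A gives ECG its own baseline, which conflicts with the TC safety baseline and may be an on-drug value for subjects treated with ELX/TEZ/IVA in the parent study

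*SAP*

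**What the plan says.** SAP 8.1 defines the baseline for long-term safety, called the TC safety baseline, as the latest non-missing value "collected before the first dose of ELX/TEZ/IVA either in the parent study or the open label study, as applicable". Protocol 12.3.1 has the same rule: the baseline "for the long-term safety analysis will be the most recent non-missing measurement (scheduled or unscheduled) collected before the first dose of ELX/TEZ/IVA", in whichever of the two studies that dose was given. In SAP Table 11-1 (Appendix A), the row for "Standard 12-lead ECG" names the TC safety baseline and refers to Section 8.1.

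Item 5 of the Derived Variables list in the same appendix then defines the ECG baseline again: "Electrocardiogram: Baseline is defined as the most recent pretreatment measurement before the first dose of study drug in the Treatment Period". This wording refers to study drug instead of ELX/TEZ/IVA, leaves out the provision for either study, and does not name a study.

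SAP 8.4.3 plans change-from-baseline summaries of the ECG intervals and heart rate, and adds: "The number and percentage of subjects meeting at least 1 threshold analysis criterion during the TE Period of OL-SS will be summarized overall". The criteria in SAP Table 11-3 include a PR criterion and two QTc criteria that depend on the increase from baseline.

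**The concern.** ECG is one of the five components of the primary safety endpoint, and the plan holds two definitions of its baseline. They agree for every subject only if item 5 is read as meaning the same thing as 8.1, which it does not say.

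The harmful case is the one in which Treatment Period means the open-label study. Subjects who received ELX/TEZ/IVA in the parent study would then be compared with an ECG taken while already on the drug. A long-term safety analysis pooled over both parent groups would mix on-drug baselines in one group with off-drug baselines in the other. Any drug effect on the ECG that arose during the parent study would be missing from the change summaries of the first group.

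**Working it through.** **What Treatment Period means.** The SAP uses the term without a qualifier in both senses.

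- Open-label sense: SAP Appendix D uses it to classify AEs against the extension's treatment-emergent period ("impute the AE start day as the day of first dose date of the Treatment Period"). The protocol synopsis likewise describes a Treatment Period of 96 weeks in this study. Where the parent period is meant, protocol 12.1 and SAP 6.2 name the parent study.
- Parent sense: item 4, directly above item 5, allows sweat chloride values "up to 30 minutes after first dose time in treatment period will be considered for baseline", and the sweat chloride baseline is the parent study baseline (SAP 8.1, Table 11-1).

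**Baseline by parent-study group**

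| Rule | ELX/TEZ/IVA in parent study | First ELX/TEZ/IVA in extension |
|---|---|---|
| SAP 8.1, protocol 12.3.1, Table 11-1 | last ECG before parent-study ELX/TEZ/IVA | last ECG before open-label ELX/TEZ/IVA |
| Item 5, open-label reading | ECG at about open-label Day 1, generally on drug | same as 8.1 |
| Item 5, parent reading | same as 8.1 | ECG from before the parent study: off drug, but older than 8.1 requires |

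The on-drug entry follows from protocol Table 3-1, footnote d: "The Day 1 Visit should be on the same day as the last scheduled visit of the parent study". Subjects who enter on a study drug interruption may be an exception.

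**Outputs exposed.** These are the change-from-baseline summaries, the PR criterion (at least 220 ms with an increase of at least 20 ms) and the QTc increases of 30-60 ms and above 60 ms. Observed values and the HR, QRS and absolute QTc criteria do not use a baseline.

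**Size under the open-label reading.** Let d be the QTcF shift already present on drug and f the share of subjects with an on-drug baseline. The error in the pooled mean change is −f × d. The documents give neither d, nor f, nor an SD, so what follows is an illustration.

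Assumptions: f = 0.5 of the 108 expected subjects; SD of change 15 ms; independent errors e; the six scheduled on-treatment ECGs (Weeks 8, 16, 24, 48, 72, 96).

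Model: change at ECG j = d + s(e_j − e_0), with s = SD/√2. Then

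P(at least one increase ≥30 ms) = 1 − E[Φ((30 − d)/s + e_0)^6], evaluated by numerical integration.

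This counts the 30-60 ms and above-60 ms criteria together. A subject with an on-drug baseline has the d = 0 probability, 9.56%. The item 5 figure is therefore 0.5 × (value at d) + 0.5 × 9.56%.

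| d (ms) | Error in mean (ms) | Correct, ≥30 ms | Item 5, ≥30 ms | Relative error |
|---|---|---|---|---|
| +10 | −5 | 29.91% | 19.73% | −34% |
| +5 | −2.5 | 17.91% | 13.73% | −23% |
| 0 | 0 | 9.56% | 9.56% | 0 |
| −5 | +2.5 | 4.53% | 7.04% | +56% |

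Sensitivity:

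- d = +10, SD 10: 9.56% against 5.13% (−46%).
- d = +10, SD 20: 44.73% against 34.10% (−24%).
- d = +10, SD 15, f = 0.4: 21.77% (−27%); f = 0.6: 17.70% (−41%).
- d = −5, SD 10: 0.13% against 0.42% (+223%, on very small percentages).
- Increases above 60 ms, SD 15: 0.24% of subjects at d = +10 and 0.02% at d = 0.

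PR is not computed, because the documents give no PR distribution. Under the parent reading no drug effect is subtracted, so this calculation does not apply.

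**The case against.** Three statements already agree on the ECG baseline, and one of them, the Table 11-1 row, is specific to ECG and sits in the same appendix as item 5. SAP 2.1 lists no modification to the protocol, so a deliberate ECG exception would contradict the SAP itself. The word pretreatment in item 5 could mean before any ELX/TEZ/IVA. Item 4 shows that the term need not refer to the extension. A careful programmer might well follow the table row. On this view item 5 is a loosely worded note, and the percentages above rest on assumed inputs whose range includes zero and both signs.

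Much of this stands. The harm is conditional on the open-label reading, and neither its size nor its direction can be established from the documents.

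The conflict itself remains. Item 5 is a derivation rule written for ECG, and the plan does not say whether it or the table row governs. SAP 8.1 applies unless otherwise specified, so item 5 can be taken as an override, which would authorise the on-drug baseline. The phrase that names the Treatment Period does not clearly support reading pretreatment as before any ELX/TEZ/IVA.

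**Conclusion.** The concern holds and should be fixed before database lock. As written, item 5 conflicts with protocol 12.3.1, SAP 8.1 and Table 11-1, and either literal reading gives one parent group a baseline other than the one 8.1 requires. The reading closer to the documents' ordinary use of the term gives subjects treated with ELX/TEZ/IVA in the parent study a generally on-drug baseline.

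The only general statement of size is that the pooled mean change is off by minus the affected share times the existing shift. The threshold percentages show how that would carry through under the stated assumptions and are not estimates for this trial. Because the safety analysis is descriptive, no test or error rate is affected.

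**What to change.** Replace the baseline sentence in item 5 with: ECG baseline is the TC safety baseline defined in Section 8.1. Keep the rules on same-day averaging for summaries and on using all reported values for thresholds. State that this baseline applies to every change-from-baseline criterion in Table 11-3.

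The cost is one SAP sentence before database lock. No new data are needed, since Section 8.1 already requires the parent-study ECGs.

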Appendix B: Imputation Rules for Missing Prior/Concomitant Medication Dates

Imputation rules for missing or partial medication start/stop dates are defined below:

1. Missing or partial medication start date:
 - a. If only DAY is missing, use the first day of the month.
 - b. If DAY and Month are both missing, use the first day of the year.
 - c. If DAY, Month and Year are all missing, use a date before the first dose date (to impute in practical, use the informed consent date).
2. Missing or partial medication stop date:
 - a. If only DAY is missing, use the last day of the month.
 - b. If DAY and Month are both missing, use the last day of the year.
 - c. If DAY, Month and year are all missing, assign ‘continuing’ status to stop date (in practical, use End of Study to impute).

In summary, the prior, concomitant, or post categorization of a medication is described below.

Table 11-1 Prior, Concomitant, and Post Categorization of a Medication

Medication Start Date	Medication Stop Date		
	< First Dose Date of Study Drug	≥ First Dose Date and ≤ End Date of TE Period	> End Date of TE Period
< First dose date of study drug	P	PC	PCA
≥ First dose date and ≤ End date of TE period	-	C	CA
> End date of TE period	-	-	A

P: Prior; C: Concomitant; A: Post

Imputation rules for missing and/or partial dates of non-pharmacological treatment/procedure will follow the same imputation rule.

Appendix C: Details of GLI Equations for Calculating ppFEV₁

Percent predicted values will be calculated for parameters of FEV₁, FVC, FEV₁/FVC, and FEF_{25%-75%} using the Quanjer GLI-2012 Regression Equations and Lookup Tables.

The regression equations and lookup tables required to implement the Quanjer GLI-2012 predicted values are available in:

Philip H. Quanjer, Sanja Stanojevic, Tim J. Cole, Janet Stocks. Quanjer GLI-2012 Regression Equation and Lookup Tables (Version 7 April 2013). Global Lung Function Initiative. [online] Available at: <http://www.ers-education.org/home/browse-all-content.aspx?idParent=138978> [Accessed Mar 26, 2018].

The instructions and tools on how to implement the Quanjer GLI-2012 equations are:

Philip H. Quanjer, Sanja Stanojevic, Tim J. Cole, Janet Stocks. Implementing GLI-2012 regression equations (Version 19 July 2015). Global Lung Function Initiative. [online] Available at: <http://www.ers-education.org/home/browse-all-content.aspx?idParent=138979> [Accessed Mar 26, 2018].

Sanja Stanojevic. GLI-2012 - SAS Macro (Version 2, 7 April 2013). Global Lung Function Initiative. [online] Available at: <http://www.ers-education.org/home/browse-all-content.aspx?idParent=138988> [Accessed Mar 26, 2018].

Data handling rule for spirometry is as follows:

- Input age with at least 2 decimal places
- Height collected at the respective visit should be used; if the height at the respective visit is not available, the last non-missing record will be used.
- For race, map the CRF reported Black or African American to Black, all other races in CRF (except White) are mapped to 'other'; multiple checks for race in CRF are also mapped to 'other'; white is a reference race in the equations and assumes 0 values for all race coefficients in the GLI equations.

